5.5.1.3 Secondary Endpoint Imputation

For spontaneous bleeds, traumatic bleeds and spontaneous joint bleeds during the 2nd 6-month period, the same procedure as described for the primary endpoint imputation will be applied in separate models.

For bleeds during the full 12-month period, a similar imputation procedure will be applied with the difference being that no restriction on bleeds such as having to be after ObsDay 182 will be made.

The same procedure will be used to impute spontaneous bleedings, traumatic bleedings, and spontaneous joint bleedings in separate models.

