5.4.2 Extended Observation Period of Efficacy

The protocol requires that for subjects that did not complete the full 364 observation days, this study should also include any post-discontinuation (post-PROPEL), bleed information provided by either the subject, or from another BAX 855 study, to augment the bleed data for the subject's missing observation period in PROPEL. To facilitate the use of this post-PROPEL data in the efficacy analysis, the extended observation period of efficacy (eOPE) is defined:

- The eOPE measured in days, is calculated as:

$$eOPE(days) = OPE(days) + (Imputation\ Start\ Date - Stop\ Date\ of\ post-PROPEL\ bleed\ data)$$

Where Stop Date of post-PROPEL bleed data is defined as the minimum of:

- Date corresponding to subject's ObsDay 364 in the PROPEL study.
- Actual recorded date of the last bleed data provided for the subject as post-PROPEL bleed data.

Imputation start date is defined as the maximum of:

- The day immediately following the date corresponding to OPE (days).
- The day immediately following the stop date of post-PROPEL bleed data.
- Date corresponding to subject's ObsDay 183.

- The eOPE in (years) is calculated from the eOPE (days) as:

$$eOPE(years) = \frac{eOPE(days)}{365.2425}$$

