5.5.1 Annualized Bleeding Rate

For all subjects who prematurely discontinued from the study (i.e., before ObsDay 364), and who refuse to provide data on bleeds for the remaining time till ObsDay 364, the number of bleeds (and hence the ABR), will be imputed for the second 6-month period, using Multiple Imputation techniques as described below. The ABR for a subject is calculated as the number of bleeds divided by the observation period under consideration (expressed in years).

The number of bleeds during the missing observation period in PROPEL, will be imputed for subjects taking into account, additional post-PROPEL bleeding information that is provided for the subject. Post-PROPEL bleeding information obtained for a subject (either by the subject or from another BAX 855 study), will be treated as if observed within PROPEL before the imputation procedures.

For simplicity, the imputation process is described below for a single subject (since the imputation will be performed on a subject specific basis), focussing on the period of interest for the primary endpoint (2nd 6-month period). The imputation process is described in step-by-step manner.

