Imputation Period (days) = (Date Corresponding to ObsDay 364 – Imputation Start Date)

Where imputation start date is as defined in section 5.4.2: Extended Observation Period of Efficacy.

- This “imputation period” will be treated/imputed as a Poisson random variate. The following example SAS[®] code can be utilized to obtain an estimate for the Poisson parameter:

```
Data <ImpSet>;  
  Set <Dataset>;  
  
  <Mu> = exp(1*<Intcpt> + <Beta1>*<sStrat> + <Beta2>*<sRace> +  
            <Beta3>*<sBAge> + <Beta4>*<sOB> + <LIP>);  
  Do i = 1 to 1 000  
    <ImpUB> = Ranpoi(1234,mu);  
    Iteration = i;  
    Output;  
  End;  
Run;
```

Where <Impset> represents the resultant dataset containing the 1 000 imputed bleed count values. <Dataset> is the input dataset containing the parameter estimates obtained from fitting the Negative binomial as discussed above and <Mu> our Poisson parameter as defined above. <Beta1>, <Beta2>, <Beta3> and <Beta4> the parameter estimates for <Stratn>, <Racen>, <BAge> and <OB> respectively. <sStratn>, <sRacen>, <sBAge> and <sOB> hold values specific to the subject being imputed, for numeric stratum category, numeric race category, baseline age and observed bleeds from ObsDay92 till last ObsDay for the subject, respectively. <LIP> is the logarithm of the imputation period (days) for the subject being imputed and <ImpUB> is the imputed number of bleeds during the imputation period for the subject.

Step3: Adding of Imputed Values to the Observed Values

The imputed bleed count of the subject is added to the subject’s observed bleed count (i.e. the subject’s observed bleeds after ObsDay 182), to obtain a bleed count for the complete 2nd 6-month period of the subject.

$$\text{Complete period bleeds} = \text{Observed period bleeds} + \text{Bleeds for imputation period}$$

For each subject to be imputed, the 1 000 imputed values will be merged into the full subject dataset, thus creating 1 000 replicates of imputed (complete) data sets (one for each imputation iteration).

Step4: Calculating ABR and Categorization

From this step onward we are working with all the subjects (those imputed and those not needing imputation) in the same dataset (1 000 replicates of them).

ABR is calculated as:

$$ABR = \frac{(Observed\ Number\ of\ bleeds + Imputed\ number\ of\ bleeds)}{Period\ under\ consideration\ in\ years}$$

Where period under consideration is:

- 1 year (365.2425 days) when working with the full year.

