The analysis of this data involves the use of a multiple imputation technique on a transformation of this data. See Section 5.5: Handling of Missing, Unused, and Spurious Data. This is the primary analysis for the PROPEL study.

The primary analysis will be repeated as a sensitivity analysis with the following alternative imputations:

- Standard uninflated imputation (excluding regular post-PROPEL bleeds).
- Imputed bleeds with the mean inflated by 10%.
- Imputed bleeds with the mean inflated by 20%.
- Imputed bleeds with the mean inflated by 40%.
- Imputed bleeds with the mean inflated by 80%.
- Worst case bleed imputation (See Section 5.5: Handling of Missing, Unused, and Spurious Data).

The proportion of subjects with total ABR <2, spontaneous ABR <2, Spontaneous ABR = 0, spontaneous AJBR <2 and spontaneous AJBR = 0, for the second 6-month period (ObsDay 183 to ObsDay364) as well as the full 12-month period treatment period (ObsDay 1 to ObsDay 364), will be analyzed in the same manner as the primary efficacy outcome. The sensitivity analysis described above for the primary efficacy outcome, will not be applicable to the secondary efficacy outcomes.

The total ABR, injury related ABR, spontaneous ABR and spontaneous AJBR, will be analyzed using a generalized linear model fitting a negative binomial distribution with logarithmic link function for the second 6-month period (ObsDay 183 to ObsDay 364) as well as the full 12-month observation period (ObsDay 1 to ObsDay 364). Separate Negative Binomial models will be used for these two time periods. The model is to include the treatment arm assigned (low level or high level), Stratum and race as fixed effects, age at baseline as continuous covariate and the logarithm of the OPE in years as an offset. The following SAS[®] code can be used to perform the analysis:

```
Proc Genmod Data = <Dataset>;
```

```
Class <Treatment> <Strat> <Race> (param=ref ref=first);  
Model <Bleeds> = <Treatment> <PREABR> <Baseline_age> <Race> / type3  
dist = negbin link = log offset = <log_OPE>;  
lsmeans <treatment> / bylevel om CL;  
ODS OUTPUT LSMEANS = <Outdata>;  
Run;
```

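### The SAP gives no 12-month imputation start date; applied as printed, the ObsDay 183 floor leaves a first-half leaver's gap counted as bleed-free in the Step 4 12-month ABR

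*SAP*

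**What the plan says.** SAP 5.5.1.1 sets out the imputation in steps for the second 6-month period. Step 2 imputes over the time from an Imputation Start Date to ObsDay 364 and takes that date from elsewhere: "Where imputation start date is as defined in section 5.4.2: Extended Observation Period of Efficacy". In SAP 5.4.2, "Imputation start date is defined as the maximum of" three dates: the day after OPE, the day after the post-PROPEL bleed data stop, and the "Date corresponding to subject's ObsDay 183". Step 4 then divides observed plus imputed bleeds by the period under consideration, which is "1 year (365.2425 days) when working with the full year".

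SAP 5.5.1.3 covers the 12-month endpoints in one sentence, under which "a similar imputation procedure will be applied with the difference being that no restriction on bleeds such as having to be after ObsDay 182" is made. No 12-month start date is given.

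SAP 7.1.2 analyses the 12-month proportions (total ABR <2; spontaneous ABR and spontaneous AJBR, each = 0 and <2) in the same way as the primary endpoint. It models the 12-month ABRs with a negative binomial regression that has "age at baseline as continuous covariate and the logarithm of the OPE in years as an offset".

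**The concern.** The denominator was adapted for 12 months, but the imputation window was not visibly adapted. The words in 5.5.1.3 about bleeds after ObsDay 182 match two places in 5.5.1.1: the dependent variable in Step 1 and the observed count added in Step 3. The floor is a rule about a date, written as ObsDay 183, in another section. A programmer who follows the text closely could lift the first two and leave the third. The Step 1 rate would then be estimated over the whole unobserved period but applied only from ObsDay 183 onward.

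The stakes are secondary. The 12-month ABRs and the proportions below a threshold are stated secondary objectives. SAP 7.1.2 says the sensitivity analyses do not apply to secondary outcomes, so nothing planned would expose the gap.

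**Working it through.** The documents give no figure for the 12-month imputation, so there is none to reproduce. The check is one of coverage.

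**Inputs**
- Start-date floor: ObsDay 183 (SAP 5.4.2).
- End of imputation: ObsDay 364 (SAP 5.5.1.1, Step 2).
- Divisor: one year (SAP 5.5.1.1, Step 4).
- Model offset: log of OPE in years (SAP 7.1.2).
- Dropout: close to 10% (SAP 2.3). Its timing is not given.
- Assumptions: constant bleed rate within a subject; no post-PROPEL data; L is the last ObsDay covered by OPE, with L < 182.

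**Floor applied: Step 4 ABR**

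Days covered = L observed + 182 imputed (183 to 364). Shortfall = 1 − (L+182)/364.

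| L | Days covered | Shortfall |
|---|---|---|
| 20 | 202 | 44.5% |
| 60 | 242 | 33.5% |
| 100 | 282 | 22.5% |
| 140 | 322 | 11.5% |

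As L approaches 0 the shortfall approaches 50%. Taking Step 2's subtraction literally (364 − 183 = 181 days) and dividing by 365.2425 changes these values by less than 1 percentage point; at L = 20 it gives 1 − 201/365.2425 = 45.0%.

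**Floor lifted**

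Coverage is 363 or 364 days for every L, so the shortfall is 0 to 0.6% depending on the day count and divisor.

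**Proportions**

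Take an illustrative 2 bleeds a year and L = 60. The probability of no imputed bleed is exp(−2 × 304/365.2425) = 0.19 with full coverage and exp(−2 × 182/365.2425) = 0.37 with the floor.

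**Arm level**

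If first-half departures are spread evenly over days 0 to 182, the mean shortfall is 0.5 − 91/364 = 0.25. Suppose dropout is 10%, all leavers withhold later data, and leavers bleed at the same rate as the others:
- half the dropout in the first 6 months: 0.10 × 0.5 × 0.25 = 1.25%;
- all of it in the first 6 months: 0.10 × 1 × 0.25 = 2.5%.

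**Negative binomial model**

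If completed counts enter with the printed offset, a leaver at day 91 has 91 + 182 = 273 days of bleeds set against 91 days of exposure, a rate 273/91 = 3 times too high. With the floor lifted and the offset unchanged it is 364/91 = 4 times too high.

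**The case against.** The strongest reply is that 5.5.1.3 already removes the floor. An imputed bleed that can fall only from ObsDay 183 is a bleed restricted to after ObsDay 182, and the words such as mark that rule as an example rather than the only thing lifted. The same section calls for the same procedure at 6 months but only a similar one at 12. SAP 5.5.1 says the steps are described, for simplicity, with the second 6-month period in view. Protocol 14.4.1 imputes the unobserved period, and Protocol 14.4.2 applies that technique to Days 1 to 364. SAP 5.8 lists no departure from this. On that reading there is no gap.

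This stands as a fair reading and is probably what was intended. A reader might infer that the SAP definitely keeps the floor for 12 months; the text does not support that. It also does not say that the floor goes, and the one defined date rule contains it. Two competent programmers could produce different 12-month results.

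The reply that few subjects are affected also stands. Only those who leave before ObsDay 182 and supply no further bleed data are exposed, and SAP 7.1.2.1 and 7.1.2.2 seek to recover such data.

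**Conclusion.** The defect is a missing definition which, if filled with the only printed rule, gives wrong Step 4 12-month ABRs and overstated 12-month proportions for first-half leavers without later data. Per affected subject the ABR shortfall is 12 to 45% for L between 140 and 20, under a constant bleed rate. For an arm's mean ABR it is about 1 to 3% under the assumed dropout timing. A between-arm comparison moves less than that if early loss is similar in both arms.

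Three stronger conclusions are not supported:
- That 45% is the ceiling. It is the value near day 20; the limit is just under 50%.
- That every 12-month bleeding result is biased toward zero. The modelled ABRs use log(OPE), not one year, so completed counts over a short OPE would push those rates up, about 3-fold for a leaver at day 91.
- That the primary endpoint is at risk. It concerns ObsDay 183 to 364, for which the floor is correct.

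This should be corrected, but it does not threaten the trial's main conclusion.

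**What to change.** Make two changes together.

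1. In SAP 5.5.1.3, state that for the full 12-month period the Imputation Start Date is the later of the day after OPE and the day after the post-PROPEL bleed data, without the ObsDay 183 limb. The 6-month definition stays as it is.
2. In SAP 7.1.2, state that for imputed datasets the model offset is the log of the completed period to which the counts refer, instead of log(OPE).

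The first change alone would enlarge the model's upward error (from 3-fold to 4-fold in the day-91 example), so the second should accompany it. The cost is a sentence in each section and a small programming change, with no new data and no effect on the primary analysis.

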5.5.2 Exposure

For the purpose of calculating weight adjusted consumption of BAX 855, missing body weight (as obtained from the *Vital Signs* eCRF panels), for a subject will be imputed with the last available measurement prior to the specific infusion. For PK parameter analysis, missing start time of infusion is a major protocol deviation and no imputation of PK infusion start time for PK parameter analysis will be performed.

Should the start time of an infusion be known and the end time of an infusion be unknown, the end time of the infusion will be imputed as five minutes after the start time of the infusion for the purpose of PK parameter calculation.

Should the end time of an infusion be known and the start time of an infusion be unknown, the start time of the infusion will be imputed as five minutes prior to the end of the infusion for the purpose of PK parameter calculation.

No imputations on infusion dates will be performed, i.e., imputations should only be performed on infusion times.

5.5.3 Adverse Events

- Causality:
A missing relationship to study medication will be considered “worst case”, as “related”.
- Severity:
 - In the event that the subject reported more than one AE under the same preferred term (PT), where one has an ‘unknown’ severity and the other a non-missing severity is recorded as ‘severe’, the missing severity will be imputed as ‘severe’.
 - In the event that the non-missing severity is ‘mild’ or ‘moderate’, the ‘unknown’ severity is to remain.

5.6 Definition of Baseline

Baseline is defined as the last non-missing (scheduled or unscheduled) measurement obtained prior to the reference start date discussed in Section 5.3: Reference Start Date, Surgery Day and Observation Days. If the date of the last non-missing assessment and the reference start date coincide, the assessment will be considered as baseline.

The following efficacy items will be making use of Baseline:

- Difference in SF-36 physical domain and component change scores from baseline to completion between treatment arms.
- Difference in change of days of physical activity participation from baseline to completion between treatment arms.
- Difference in the change in healthcare resource utilization from baseline to completion between treatment arms.
- Within treatment arm change in the HJHS total score from Baseline to Completion.
- Within treatment arm change and between treatment arm change in Haemo-SYM total score as well as bleed and pain severity between baseline and completion.
- Within treatment arm change and between treatment arm change in EQ-5D utility total score as well as VAS score between baseline and completion.

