9.1.2 Inclusion Criteria for Newly Recruited Subjects

Newly recruited subjects including BAX 855 naïve subjects who meet **ALL** of the following criteria are eligible for this study:

1. Subject is 12 to 65 years old at the time of screening
2. Subject has severe hemophilia A (FVIII clotting activity $< 1\%$) as confirmed by central laboratory OR by historically documented FVIII clotting activity performed by a certified clinical laboratory, optionally supported by a FVIII gene mutation consistent with severe hemophilia A
3. Subject has been previously treated with plasma-derived FVIII concentrates or recombinant FVIII for ≥ 150 documented EDs
4. Subject is either receiving on-demand treatment or prophylactic treatment and had an annual bleeding rate of ≥ 2 documented and treated during the past 12 months
5. Subject has a Karnofsky performance score of ≥ 60 at screening
6. Subject is HIV-; or HIV+ with stable disease and CD4+ count ≥ 200 cells/mm³, as confirmed by central laboratory at screening
7. Subject is hepatitis C virus negative (HCV-) by antibody (if positive, additional PCR testing will be performed), as confirmed by central laboratory at screening; or HCV+ with chronic stable hepatitis
8. If female of childbearing potential, subject presents with a negative urine pregnancy test and agrees to employ adequate birth control measures for the duration of the study
9. Subject is willing and able to comply with the requirements of the protocol

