13.9 Vital Signs

Vital signs will include body temperature (°C or °F), respiratory rate (breaths/min), pulse rate (beats/min), and systolic and diastolic blood pressure (mmHg). Height (in or cm) and weight (lb or kg) will also be collected at screening; weight will also be recorded before any IP infusions are administered at the study site, but at least at each study visit. Blood pressure will be measured when subjects are in the supine position.

Vital signs will be assessed within 15 minutes prior to start of infusion and 30 ±5 minutes following infusion at baseline and at each study visit. Vital signs should always be assessed before any blood sampling is done at a particular timepoint.

Vital sign values are to be recorded on the CRF. For each abnormal vital sign value, the investigator will determine whether or not to report an AE (see definition in Section 13.2 and record the medical diagnosis (preferably), symptom, or sign on the AE CRF). Additional tests and other evaluations required to establish the significance or etiology of an abnormal value, or to monitor the course of an AE should be obtained when clinically indicated. Any abnormal value that persists should be followed at the discretion of the investigator.

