5.3 Reference Start Date, Surgery Day and Observation Days

5.3.1 Reference Start Date

Reference start date is defined as the day of the subject's first BAX 855 PK-guided prophylactic infusion, after enrolment in the 261303 protocol (henceforth referred to as the PROPEL study) and will be referred to as ObsDay 1. Subjects who discontinue study participation prior to receiving any BAX 855 prophylactic administration in the PROPEL study are not to have a reference start date.

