8.4 Vital Signs

Subject listings will be presented for vital signs including a breakdown for abnormal vital signs using the SAS. A summary table and shift table will be presented for vital signs using the SAS by age group and alphabetic parameter.

The following information items are obtained from the eCRF:

- Vital signs (Vital Signs eCRF panels) for parameters:
 - Body temperature (°C).
 - Diastolic blood pressure (mmHg).
 - Pulse rate (beats/minute)
 - Respiratory rate (breaths/minute).
 - Systolic blood pressure (mmHg).
 - Weight (kg).

The following derivations will be made based of the eCRF reported results:

- A result will be considered out of range if the observed result is less than the lower limit of the normal range (indicated as “L”) or larger than the upper limit of the normal range (indicated as “H”). The normal ranges to be used are:

Table 12 Vital Signs Parameter Ranges

Parameter	Age Range (Years)	
	≥13	≥6 to <12
Respiratory rate (breaths/minute)	5 to 16	14 to 22
Pulse rate (beats/minute)	55 to 100	60 to 95
Systolic blood pressure (mmHg)	90 to 140	100 to 120
Diastolic blood pressure (mmHg)	50 to 89	60 to 75
Body temperature (Celcius)	35 to 37.9	35 to 37.9

- Identification of clinically significant vital signs for inclusion in the vital signs presentations, will be obtained from the Shire medical team following their review of the AE and vital signs data.

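### The date-only baseline rule takes the post-infusion vital signs as baseline for the shift table, and the vital-sign range table has no range for age 12

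*SAP*

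**What the plan says.** **Baseline.** SAP 5.6 opens: "Baseline is defined as the last non-missing (scheduled or unscheduled) measurement obtained prior to the reference start date". It then extends this to the day itself: "If the date of the last non-missing assessment and the reference start date coincide, the assessment will be considered as baseline". Both sentences work on dates; neither mentions clock time or the infusion. SAP 5.3.1 fixes the reference start date as the day of the subject's "first BAX 855 PK-guided prophylactic infusion, after enrolment in the 261303 protocol". SAP 5.6 is the only definition of baseline in the SAP.

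**Timing of vital signs.** Protocol 13.9 has them assessed "within 15 minutes prior to start of infusion and 30 ±5 minutes following infusion at baseline and at each study visit". The Baseline Visit flow in Protocol 21.2 and the schedule in 21.3 agree.

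**Outputs.** SAP 8.4: "A summary table and shift table will be presented for vital signs using the SAS by age group and alphabetic parameter".

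**Flags.** SAP 8.4 compares each observed value with a fixed range: "A result will be considered out of range if the observed result is less than the lower limit of the normal range", with the matching rule for the upper limit. The ranges stand in Table 12 of that section (a second Table 12, of PK parameters, is in SAP 9.2). Its two age columns are ≥13 and ≥6 to <12 years.

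**Eligible age.** Protocol 9.1.2: "Subject is 12 to 65 years old at the time of screening". A footnote to Protocol 8.2 admits subjects from the pediatric study once they are at least 12 at consent.

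**The concern.** A shift table asks how a subject's status under treatment compares with status before it. If the reference value was taken half an hour after the first PK-guided dose, a transient rise or fall at that dose becomes the reference category. Later ordinary values then appear as the shift.

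The range table has a different fault. The SAP supplies the vital-sign limits itself, whereas laboratory ranges come from the central laboratory. No other source fills a missing age band, so a subject assigned age 12 has no limits to be compared with.

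Changes in vital signs are a named secondary safety outcome, and the trial has no data monitoring committee. The descriptive safety tables should therefore say what they appear to say.

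**Working it through.** The plan states no figure on this point, so the check applies its rules literally.

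**1. Which reading becomes baseline.**
- Readings on the reference start date, in minutes relative to the infusion (Protocol 13.9): pre-infusion at −15 at the earliest, post-infusion at about +30.
- Rule as written: the last non-missing value, with same-day values allowed. max(−15, +30) = +30, the post-infusion reading.
- Rule with a time condition (value taken before the infusion starts): only −15 qualifies, the pre-infusion reading.

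**2. What this does to a shift table.** The following values are assumed for illustration: systolic pressure 125 mmHg before the first PK-guided infusion, 85 after it, and 120 at the next visit. The Table 12 range for age ≥13 is 90 to 140.

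| | Rule as written | With pre-infusion condition |
|---|---|---|
| Baseline value | 85 | 125 |
| Baseline category | L | normal |
| Shift at next visit | L to normal | normal to normal |
| Change from baseline | 120 − 85 = +35 | 120 − 125 = −5 |

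The reading of 85 is marked L under both rules, because the flag compares it with 90 and not with baseline.

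**3. Which other safety variables are exposed.** In the Baseline Visit flow of Protocol 21.2, hematology, chemistry, lipid and immunogenicity samples are drawn only before the infusion. The date rule does no harm there. Vital signs are the safety variable measured on both sides of the dose.

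**4. Ages without a range.** Whole-year ages 12 to 65 are 65 − 12 + 1 = 54 values. Ages 13 to 65 fall in the ≥13 column (53 values). No eligible age falls in ≥6 to <12. Age 12 falls in neither, so one value is uncovered.

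**5. Who counts as 12.** SAP 8.4 does not say which age selects the column. SAP 6.2 derives age as the year of the reference start date minus the year of birth. Under that formula a true 12-year-old gets 12 if the birthday has already come round in the start year, and 13 if it has not. Assuming birthdays and start dates spread evenly over the year, a simulation of 200,000 subjects truly aged 12 gave 50.1% derived as 12 (no range) and 49.9% derived as 13 (the ≥13 range). With exact age, all of them would lack a range for as long as they are 12.

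**The case against.** The strongest reply is that the SAP does not expressly send vital signs through 5.6. That section lists only efficacy items as users of baseline. SAP 8.4 does not define the shift table's baseline or timepoints, and the table layouts are in the Output Templates, which are not part of these documents. A table split by pre- and post-infusion timepoint could avoid the problem. Nothing says a post-infusion baseline is intended, and SAP 5.10 separately defines a within-visit change from pre-infusion, so its authors knew the distinction.

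This limits the certainty about the final table but does not remove the defect. A shift table needs a baseline, 5.6 is the only one on offer, and a programmer following it has no instruction to prefer the pre-infusion value.

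Three stronger readings are tempting, and the documents do not support them.

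- *That the baseline rule produces wrong L/H flags.* Baseline is not an input to the flag.
- *That a reaction to the first PK-guided dose would vanish.* An out-of-range post-infusion value is still flagged wherever a range exists, and all values are listed. The change from pre-infusion would show it if that calculation is produced for vital signs. The investigator must consider an AE for each abnormal value (Protocol 13.9). For most subjects this infusion is also not the first exposure in the study: the PK infusion comes earlier, with its own readings before and after.
- *That no 12-year-old can ever be flagged or reviewed.* The calendar-year formula may place about half of them in ≥13. If age at visit is used, subjects turn 13 during the 12 months of treatment. Clinical significance is set by the sponsor's medical review, which depends on neither rule. Body temperature has the same limits in both columns, so the gap matters little there.

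**Conclusion.** Both faults stand as errors in the written rules, with limited reach.

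The baseline fault can affect every subject who has both readings at the Baseline Visit, which the protocol schedules for all. It reaches the baseline category in the vital-sign shift table and any change from baseline. This rests on a literal reading of 5.6 and on the inference that the shift table uses it.

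The range fault affects subjects assigned age 12. Their L/H status is undefined rather than wrong. Their number is not given, and it depends on an age definition that the SAP leaves open.

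Only descriptive safety output is involved. The primary endpoint and the planned hypothesis tests are not affected.

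**What to change.** 1. **SAP 5.6.** State that, for variables measured before and after infusion, baseline is the last non-missing value taken before the start of the first PK-guided infusion. Keep this to such variables. The joint score is also done at the Baseline Visit, where Protocol 21.2 lists it after the infusion steps, so a blanket time condition could discard a valid baseline. State also whether a post-infusion reading from the earlier PK assessment may serve if the pre-infusion one is missing.
2. **SAP 8.4, Table 12.** Make the age bands contiguous so that age 12 is covered, with the limits chosen by the sponsor's medical team. Drop any column that fits no eligible subject.
3. **SAP 8.4.** Say which age assigns the range: exact age at consent, exact age at the visit, or the calendar-year age of 6.2.

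The cost is SAP wording, one programming condition and a table edit. No new data are needed, because the pre- and post-infusion readings are already scheduled as separate timepoints.
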